### 8.1.6 Final examination (month 30)

Medical history (incl. assessment of B-symptoms)
Clinical examination (including palpation of lymph node regions, skin reaction in the radiation area)
ECOG-Performance status
Laboratory testing:
- Differential blood cell count (hemoglobin, leucocytes, thrombocytes, neutrophils, lymphocytes)
- Clinical chemistry (sodium, potassium, calcium, AST/ALT, total bilirubin, alkaline phosphatase, creatinine)
- LDH
- Total protein, protein-electrophoresis
- $\beta$ 2 microglobuline
CT or MRI ( $\leq$ 4 months), if necessary: additional ultrasound
- head&neck
- thorax
- abdomen
- pelvis including inguinal region
Site specific examinations:
Thyroid testing in case of cervical or supraclavicular lymphoma (TSH, ft3/ft4)
Assessment of AEs

### 8.1.8 Genetic and molecular testing of the initial lymph node biopsy (additional scientific program)

Genetic and molecular investigations (e.g. p53 mutations, bcl2 transformation, genetic profiling testing for mutations on several sites) in relation to lymphoma disease are planned on the initial biopsy specimen as additional scientific program. These investigations are planned and coordinated by the pathology panel of the GLSG. All investigations should serve the increase of knowledge about origin, expansion and therapy of malignant lymphomas. There might be new scientific questions/methods concerning the aim of the study, which cannot be addressed today (e.g. knowledge of a new genetic mutation in follicular lymphomas, new measurement tools, which allow a more sensitive evaluation of MRD,...). For this reason, blood and tissue samples should be stored for an unlimited time or until the draw back of the patients consent.

## **8.2 FDG-PET/CT**

The FDG-PET/CT within the trial should be performed according to the recommendations of Juweid et al.[49]

- There should be at least 5 weeks interval after a surgical intervention (e.g. lymph node extirpation)
- No use of „non attenuation PET scans“
- FDG dosage 3.5 – 8 MBq/kg body weight with a minimal dose of 185 MBq
- 4 hours fasting before FDG injection
- Glucose level < 200 mg/dL at the time of injection
- Primary staging FDG-PET/CT: Whole body scanning 60 +/- 10 minutes after FDG injection;  
Week 18: Whole body PET scanning, CT scanning of the initially involved regions
- contrast enhancing agents are not mandatory for the CT imaging
- Oral contrast agent might be used for better differentiation of bowel and other structures

The interpretation of the initial staging PET should be done using visual assessment, with PET/CT images scaled to fixed SUV display and color table [50]

## **8.3 Efficacy Parameters**

### 8.3.1 Criteria of Remission of the FDG-PET (metabolic remission)

The metabolic remission criteria of the PET scan is according to the revised Cheson criteria of 2014 under the use of the 5-PS score [50, 62].

The 5-PS scores the most intense uptake in a site of initial disease, if present, as follows:

- Score 1: No uptake
- Score 2: Uptake  $\leq$  mediastinum
- Score 3: Uptake  $\geq$  mediastinum but  $\leq$  liver
- Score 4: Uptake moderately higher than liver
- Score 5: Uptake markedly higher than liver and/or new lesions
- Score X: New areas of uptake unlikely to be related to lymphoma

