## STUDY FLOW CHART

Two stage Screening:

- Histology and CT or MRI: centrally approved follicular lymphoma grade 1/2 in clinical stage I/II (max. 93 patients)
- FDG-PET/CT: exclusion of stage III/IV patients (approx. 15%= 14 patients)  
Inclusion of max 79 patients: ca. 70% (=55 patients with remaining lymphoma); approx. 30% (=24 patients with metabolic CR)  
Drop-out-rate: approx. 10% (analyzable for primary endpoint 50 patients with remaining PET positive lymphoma)

\* = centrally reviewed

PET-pos (PET+): PET positive residual lymphoma  
 PET-neg. (PET-): metabolic CR  
 W: week  
 FU: Follow-up examinations  
 morph. SD: morphological SD

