### Role of FDG-PET

The routine staging diagnostic procedures using CT/MRI will be augmented by a FDG-PET/CT examination in the GAZAI trial. The total radiation dose will then be defined response adapted by a second FDG-PET.

Since the sensitivity and specificity of FDG-PET is higher compared to sole morphological imaging, all patients will get an initial FDG-PET/CT. This has to be performed at least 5 weeks after a surgical procedure (e.g. lymph node sampling) for minimizing the risk of false positive results.

LDRT alone of the involved lymph nodes regions results in responses shown in Table 2. However, LDRT alone leads less often to a CR than a full dose radiation therapy in these patients (see Table 1 and 2 and the FORT trial).

Since a negative FDG-PET is an independent predictive factor regarding PFS [7, 51], the decision for or against salvage radiation will be done based on a restaging FDG-PET/CT (FDG-PET positive: salvage RT of additional 18 x 2 Gy; FDG-PET negative: no salvage RT).

Since only patients with initially PET positive lymph nodes are valuable for the evaluation of the primary endpoint (metabolic CR rate after LDRT and anti-CD20 antibody), the FDG-PET in week 18 can be omitted in case of FDG-PET negativity at the initial staging (e.g. all macroscopic pathological lymph nodes were surgically removed).

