## 7.3 Salvage irradiation (week 20-23)

All patients with PET positive lymphoma before the first Gazyvaro administration (initial FDG-PET/CT), will get an additional FDG-PET/CT in week 18 which should be sent to the trial center in Heidelberg. All of those patients who do not show a morphologic CR/PR or do not have a metabolic CR will get a salvage irradiation starting in week 20.

The target volume is identical to the initial LDRT irradiation in week 9. The dose is 18 x 2 Gy (ICRU 50). The same positioning devices, the same planning CT and the same treatment plan as for the LDRT should be used (see above).

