### **Complete Metabolic Response (CMR)**

Score 1 and score 2.

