### **Partial Metabolic Response (PMR)**

Score 3, 4 or 5 with reduced uptake compared with baseline and residual mass(es) of any size

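### Section 8.3.1: Scores 2 and 3 both include uptake equal to mediastinum, so the restated PET scale is ambiguous at the cut-off for complete metabolic response (minor)

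*Combined protocol and SAP*

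**What the plan says.** Section 8.3.1 bases metabolic remission on the 2014 criteria with the five-point scale and then writes the scale out. The lines that matter are "Score 2: Uptake $\leq$ mediastinum", "Score 3: Uptake $\geq$ mediastinum but $\leq$ liver" and "Score 4: Uptake moderately higher than liver".

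The response categories follow from the score. CMR is "Score 1 and score 2". Partial metabolic response (PMR) is "Score 3, 4 or 5 with reduced uptake compared with baseline and residual mass(es) of any size".

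The metabolic result at week 18 is used in three places:

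- **Primary endpoint.** Sections 2.2 and 11.2 make metabolic CR at week 18 the primary endpoint.
- **Treatment.** Section 7.3 says that patients "who do not show a morphologic CR/PR or do not have a metabolic CR will get a salvage irradiation starting in week 20". Section 1.2 (Role of FDG-PET) gives the rule by PET status: "FDG-PET positive: salvage RT of additional 18 x 2 Gy; FDG-PET negative: no salvage RT". The study flow chart links the two terms: "PET-neg. (PET-): metabolic CR".
- **Subgroups.** Section 2.1 plans to report PFS and site of recurrence separately for patients who are PET negative and PET positive in week 18.

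The week-18 PET is centrally reviewed (Sections 8.1.4 and 14.2). Section 14.2 names the reviewing specialties but no rule for a tie. Section 8.2 prescribes visual assessment for the initial staging PET only.

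**The concern.** A response scale should place every scan in exactly one score. Here two neighbouring scores share a boundary value, and that boundary separates CMR from PMR. Two readers could agree that residual uptake equals mediastinum, both follow the printed scale, and still record different primary-endpoint outcomes.

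For the patient, the consequence can be 36 Gy of further radiotherapy. Limiting full-dose radiotherapy to patients who need it is the purpose of the trial, so the line that triggers it should be clear. Timing matters as well. Salvage starts in week 20, whereas Section 11.4 requires the SAP to be final only before database lock. A tie rule set in the SAP could come after patients had been treated.

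**Working it through.** **1. Boundary check.** Take illustrative values of 2.0 for mediastinum and 3.0 for liver, and test residual uptake against the printed definitions.

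| Uptake | Score 2 (≤ mediastinum) | Score 3 as printed (≥ mediastinum, ≤ liver) | Score 3 as corrected (> mediastinum, ≤ liver) |
|---|---|---|---|
| 1.9 | yes | no | no |
| 2.0 | yes | yes | no |
| 2.1 | no | yes | yes |

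The overlap is the single value equal to mediastinum, and the corrected symbol removes it. At the liver boundary there is no overlap: equality belongs to Score 3, and Score 4 starts above liver.

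**2. Which scans are affected.** PMR also requires reduced uptake and a residual mass. The ambiguity between CMR and PMR therefore concerns tied scans with both features. A tied scan without a residual mass does not meet the PMR definition and is left out here.

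**3. Effect on treatment.** Inputs are from Sections 7.2 and 7.3.

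- Without salvage: 2 × 2 Gy = 4 Gy.
- With salvage: 4 + 18 × 2 = 40 Gy.
- With morphologic CR or PR, the score decides between the two.
- Without morphologic CR or PR, salvage is given in any case, and only the classification is affected.

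**4. The plan's own precision figure.** Section 11.1 assumes a CR rate of 60% and n = 50. The asymptotic half-width is 1.96 × √(0.6 × 0.4 / 50) = 13.6 points, against the stated figure of about 13.5. It is reproduced and does not depend on the tie.

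**5. Effect on the CR rate.** One tied scan moves the rate by 1/50 = 2.0 points, or by 1/55 = 1.8 points if all 55 patients starting treatment are counted. The Wilson 95% interval named in Section 11.4 is

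(p + z²/2n ± z√(p(1 − p)/n + z²/4n²)) / (1 + z²/n), with z = 1.96.

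The number of ties below is assumed, because the documents give none.

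| Tied scans moved from CMR to PMR | CR rate, n = 50 | Wilson 95% CI |
|---|---|---|
| 0 | 30/50 = 60.0% | 46.2 to 72.4% |
| 1 | 29/50 = 58.0% | 44.2 to 70.6% |
| 3 | 27/50 = 54.0% | 40.4 to 67.0% |
| 5 | 25/50 = 50.0% | 36.6 to 63.4% |

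To exceed the planned half-width, ties read the same way would have to number more than 13.6 / 2.0 = 6.8, so seven (14.0 points). The Wilson half-width stays between 13.1 and 13.4 points over the rows shown.

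**The case against.** The strongest reply is that this is a slip with an evident meaning. Score 2 expressly includes equality with mediastinum, and at the liver boundary equality goes to the lower score. A specialist would probably score a tie as 2. This largely stands, and it is why the point is minor. It does not remove the overlap, because no section says that the lower score applies.

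A second reply is that the symbol may have been misread from the PDF. That cannot be excluded. However, the text keeps > and ≥ apart elsewhere, for example in the age and lesion-size lines of Section 8.1.2, so nothing indicates a misread.

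A third reply is that the cited 2014 criteria may settle equality. They cannot be checked here. The point therefore goes only to the protocol's restatement.

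Three stronger readings are tempting, and the documents do not support them:

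- **The endpoint is undefined, or one patient holds two responses at once.** The reviewer assigns a score and the response follows from it. The ambiguity is in choosing between Scores 2 and 3, and the list itself points to the likely answer.
- **The trial's conclusion is at risk.** Section 11.1 states that no formal hypothesis is tested, Section 11.5 plans no interim analysis, and no tie frequency is given. Nothing supports a material shift in the CR rate.
- **The salvage rule is separately defective.** Section 7.3 already depends on metabolic CR, which Section 8.3.1 defines. Nothing suggests that the endpoint and the salvage decision would use different readings.

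**Conclusion.** The scale is wrong as printed, and the point is minor. Scores 2 and 3 overlap at uptake equal to mediastinum, which is the CMR cut-off. The restated scale is therefore ambiguous for a week-18 scan with that uptake, reduced from baseline, and a residual mass.

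The consequence for one patient can be large: 4 Gy or 40 Gy, provided morphologic CR or PR is reached. The same score places the patient in the PET-negative or PET-positive subgroup of Section 2.1. The consequence for the trial is probably small, at 2.0 points per tied scan at n = 50, with the number of ties unknown. Sample size, planned precision and statistical decisions stay as they are.

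This rests on two assumptions: that the printed ≥ is what the source document contains, and that no instruction outside the supplied documents already settles ties.

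**What to change.** After confirming the symbol in the source PDF, change Score 3 in Section 8.3.1 to uptake > mediastinum but ≤ liver. Equality with mediastinum is then Score 2, hence CMR, which matches how the list treats the liver boundary. Apply the correction before week-18 scans are read, since the score decides treatment from week 20.

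The cost is one symbol. Section 7.3 needs no added sentence, because it takes its meaning from metabolic CR. Visits, sample size and analysis methods are unchanged.

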### **Complete Metabolic Response (CMR)**

Score 1 and score 2.

### **Partial Metabolic Response (PMR)**

Score 3, 4 or 5 with reduced uptake compared with baseline and residual mass(es) of any size

**Metabolic Treatment Failure / Metabolic Progressive Disease (MPD)**

An increase in FDG uptake to a score of 5, score 5 with no decrease in uptake, and new FDG-avid foci consistent with lymphoma

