**Stable Disease (SD)**

Stable disease is defined as less than a PR but is not progressive disease

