### 11.6 Definition of Target Variables

Progression-free survival:

- a) Calculated from start of therapy up to the time of progression (morphologic or metabolic) or death
- b) Calculated from start of therapy up to the time of progression (morphologic or metabolic) or death in patients with initially remaining lymphoma (morphologic or metabolic)

Overall survival:

Calculated from start of therapy up to the time of death

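### As written, unchanged score-5 FDG uptake at week 18 is metabolic progression and so a PFS event, before the planned salvage step begins

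*Combined protocol and SAP*

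**What the plan says.** Section 8.3.1 gives three metabolic categories.

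- Complete metabolic response: "Score 1 and score 2".
- Partial metabolic response: "Score 3, 4 or 5 with reduced uptake compared with baseline and residual mass(es) of any size".
- A combined category headed "Metabolic Treatment Failure / Metabolic Progressive Disease (MPD"), defined as "An increase in FDG uptake to a score of 5, score 5 with no decrease in uptake, and new FDG-avid foci consistent with lymphoma".

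There is no metabolic category for unchanged disease. The CT/MRI scale in section 8.3.2 has one: "Stable disease is defined as less than a PR but is not progressive disease".

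Section 11.6 defines PFS (a) as "Calculated from start of therapy up to the time of progression (morphologic or metabolic) or death". Definition (b) uses the same event "in patients with initially remaining lymphoma (morphologic or metabolic"). It does not refer back to 8.3.1 and gives no other meaning for metabolic progression.

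Under section 7.3, patients who are PET positive before the first infusion "will get an additional FDG-PET/CT in week 18". Those without metabolic CR, or without morphologic CR or PR, go on to salvage irradiation from week 20. Section 11.4 plans Kaplan-Meier estimates of 2-year PFS with Greenwood intervals. Section 2.1 uses PFS as one measure of success of the response-adapted approach and names three subgroups, one being patients still PET positive at week 18.

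**The concern.** The combined category puts lack of response and growth of disease under one label, and section 11.6 turns that label into a PFS event. A patient in whom nothing has grown and nothing new has appeared can therefore be recorded as progressed at week 18.

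This matters for three reasons. First, salvage irradiation is part of the strategy under study, and for these patients the PFS clock stops before it is given. Second, patients with unchanged disease are handled differently according to the height of the uptake and the imaging scale: an event at score 5, no category at score 3 or 4, and no event for stable disease on CT/MRI. Third, in the subgroup still PET positive at week 18, PFS would partly repeat the scan that defines the subgroup instead of describing outcome after salvage.

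**Working it through.** **Step 1: the plan's own figures.** Section 11.1 gives a chain of patient numbers and a confidence interval half width. Both reproduce.

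- 93 × 0.85 = 79.05 (stated 79); 79 × 0.70 = 55.3 (stated 55); 55 × 0.90 = 49.5 (stated 50).
- 1.96 × √(0.60 × 0.40 / 50) = 0.1358 (stated as about 13.5%).

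None of these is in dispute. The figures 79 and 55 serve as denominators below.

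**Step 2: applying the categories.** Each row is a possible week-18 PET result without new foci, classified with the wording of 8.3.1. The combined definition is read as a list of alternatives, because a score cannot both rise to 5 and be an unchanged 5.

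| Change from baseline | CMR | PMR | MPD | PFS event from PET under 11.6 |
|---|---|---|---|---|
| Score 5, unchanged | no | no (not reduced) | yes | yes |
| Score 5, rising further within 5 | no | no | yes | yes |
| Score 4, unchanged | no | no | no | no |
| Score 3, unchanged | no | no | no | no |
| Score 3 rising to 4 | no | no | no | no |
| Score 5, reduced but still 3 to 5 | no | yes | no | no |

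The first row is the problem. Rows three to five have no category at all. No section exempts the week-18 scan, or patients going on to salvage, from the PFS event rule.

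**Step 3: effect of one patient.** Suppose there is no censoring and the patient would otherwise be event-free at 2 years. The loss is then 1/N.

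- Definition (a), 79 patients starting therapy: 1/79 = 1.27 points.
- Definition (b), taking the 55 PET-positive patients: 1/55 = 1.82 points. Definition (b) also admits purely morphologic residual disease, so its denominator may exceed 55 and the loss be slightly smaller.
- Subgroup still PET positive at week 18, at the planned 60% CR rate: 0.40 × 55 = 22 patients, so 1/22 = 4.5 points.

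**Step 4: range.** The share of non-CR patients with unchanged score 5 is not in the documents, so the shares below are assumptions. For illustration, 2-year PFS is otherwise set at 86% for everyone, the MIR figure in section 1.1.5. The number affected is 22 × share, and the resulting PFS is 86 × (1 − number/N).

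| Assumed share of the 22 | Patients | Counted as events at week 18, of 79 / of 55 | 2-year PFS (a) | 2-year PFS (b) |
|---|---|---|---|---|
| 0% | 0 | 0 / 0 points | 86.0% | 86.0% |
| 10% | 2.2 | 2.8 / 4.0 points | 83.6% | 82.6% |
| 25% | 5.5 | 7.0 / 10.0 points | 80.0% | 77.4% |
| 50% | 11 | 13.9 / 20.0 points | 74.0% | 68.8% |

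Even in the last row the net loss is 86.0 − 74.0 = 12.0 points for (a) and 86.0 − 68.8 = 17.2 points for (b). Section 1.1.6 reports much lower PFS in PET-positive patients in two other trials (33% at 42 months and 35% at 3 years). If the affected patients resembled those, many would have had an event anyway and the net loss would be smaller.

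**The case against.** The best defence is that the heading in 8.3.1 joins two labels, treatment failure and progressive disease, while 11.6 counts only progression and does not cite 8.3.1. On that reading the sponsor may always have meant only rising uptake or new foci. But the two labels share one definition and one abbreviation, and this is the only definition of metabolic progression available. An analyst deriving PFS from the text would count the event; one who guessed at the intent would not. That needs correcting either way.

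It can also be said that the trial is descriptive, that definition (b) and the subgroups in 2.1 would make the effect visible, and that the SAP announced in 11.4 can settle event rules before database lock. All of this is true. It limits the damage and makes the repair easy, but it does not make the rule right.

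Some stronger inferences are tempting and do not hold:

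- **That all metabolically stable patients count as progressed.** Only those at score 5 do.
- **That the rule spoils a PFS comparison with MIR.** No such comparison is planned. The historical comparisons named are morphologic response, quality of life and MRD (sections 1.2, 2.1 and 2.3).
- **That PFS is the main secondary endpoint.** The secondary endpoints are unranked.
- **That Table 2 gives the number affected.** With 80 to 95% responding, one might infer 5 to 20% unchanged. The table concerns 2 × 2 Gy alone, largely in advanced, recurrent or pretreated disease, and its non-responders may include true progressors. It gives no frequency of unchanged score-5 uptake after antibody plus irradiation.

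**Conclusion.** Wrong as written, and it should be changed. Read literally, unchanged score-5 uptake at week 18 without new foci is a PFS event in both definitions. Stable disease on CT/MRI is not, and unchanged score 3 or 4 is unclassified.

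The effect is confined to 2-year PFS and to the subgroup still PET positive at week 18. The primary endpoint is untouched, because such a patient is not a complete metabolic responder under any labelling, and the salvage decision does not use the category.

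The size is about 1.3 points per patient in definition (a) and about 1.8 in definition (b). This rests on the planned 79 and 55 patients and on the patient being otherwise event-free at 2 years. The total is unknown and may be zero.

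**What to change.** In 8.3.1, split the combined category.

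- *No metabolic response*: score 3, 4 or 5 with no significant change from baseline uptake and no new foci. State the threshold for change, and use the same threshold in the partial response definition so that the two do not overlap.
- *Metabolic progressive disease*: an increase in uptake from baseline with score 4 or 5, including a further increase within score 5, or new FDG-avid foci attributable to lymphoma.

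Before finalising, check that every combination of score and change falls into exactly one category, including an increase that still ends at score 3.

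In 11.6 or the SAP, state that only metabolic progressive disease is a metabolic PFS event. Report a sensitivity analysis that also counts no metabolic response at score 5 as an event.

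The cost is a wording change and one extra category on the PET read form, with no new scan, visit or reader. PFS will have slightly fewer events. The response-adapted treatment path stays as it is.

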**8.3.2 Criteria of Remission of CT/MRI**

The morphologic remission is according to the NCI criteria [63].

**Complete Response (CR)**

All lymph nodes and nodal masses must have regressed to normal size ( $\leq 1.5$  cm in their greatest transverse diameter for nodes  $\geq 1.5$  cm before therapy). Previously involved nodes that were 1.1 to 1.5 cm in their greatest transverse diameter before treatment must have decreased to  $\leq 1$  cm in their greatest transverse diameter after treatment, or by more than 75% in the sum of the products of the greatest diameters (SPD).

